### **3.5 SURGICAL GUIDELINES**

In some cases, participants may require placement of brachytherapy catheters at the time of surgical resection. This will be coordinated by the referring oncologist or surgeon. Surgical therapy is not included on this protocol

### **3.6 RADIATION THERAPY GUIDELINES**

This protocol involves radiation therapy given as HDR brachytherapy. In some cases, participants may also need to receive external beam radiation therapy. Generally, participants are expected to receive their standard external beam radiation therapy care by their referring oncologist. Occasionally, however, participants may not have timely or appropriate access to care at home, and in these rare cases, the external beam component may be provided at the NCI ROB clinic.

### **3.7 COST AND COMPENSATION**

#### **3.7.1 Costs**

NIH does not bill health insurance companies or participants for any research or related clinical care that participants receive at the NIH Clinical Center. If some tests and procedures performed outside the NIH Clinical Center, participants may have to pay for these costs if they are not covered by insurance company. Medicines that are not part of the study treatment will not be provided or paid for by the NIH Clinical Center.

#### **3.7.2 Compensation**

Participants will not be compensated on this study.

#### **3.7.3 Reimbursement**

The NCI will cover the costs of some expenses associated with protocol participation. Some of these costs may be paid directly by the NIH and some may be reimbursed to the participant/guardian as appropriate. The amount and form of these payments are determined by the NCI Travel and Lodging Reimbursement Policy.

### **3.8 CRITERIA FOR REMOVAL FROM PROTOCOL THERAPY AND OFF STUDY CRITERIA**

#### **3.8.1 Criteria for removal from protocol therapy**

Prior to removal from study, effort must be made to have all subjects complete a safety visit approximately 30 days following the last dose of study therapy.

Protocol therapy is complete when the participant has completed the brachytherapy component of treatment. This will vary depending on the site of disease treated, see [Appendix A](#).

#### **3.8.2 Off Study Criteria**

##### **3.8.2.1 Administrative**

Participants who are removed from the study for non-medical or administrative reasons prior to the completion of the active course of treatment may be replaced. A participant may be taken off study for the following non-medical or administrative reasons:

- Participant refusal of further treatments (reasons must be noted in the participant's records).
- We are no longer able to maintain contact with the participant and/ or their oncologist.
- It is deemed in the best interest of the participant by the PI.
- Serious protocol deviation as determined by the PI.
- Participant loses capacity to provide consent.

### 3.8.2.2 Toxicity

Any participant who develops a grade 4 toxicity considered primarily due to the study treatment. However, the toxicity will be followed to assess the duration and resolution.

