### 3.8.2.3 Tumor Progression

Any participant with clinical or radiographic evidence of progressive disease during the active course of treatment will be removed from the study if it is deemed by the PI that additional therapy would not be in the best interest of the participant.

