### 3.8.2.4 Concurrent Illness

The development of a concurrent serious medical condition that might preclude or contraindicate the further administration of radiation therapy.

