### 3.8.2.5 Completion

- The completion of HDR and 12 months follow up
- The participant is unable to complete the radiation treatment process for any reason or is non-compliant with the treatment &/ or follow- up requirements
- Follow-up is no longer deemed necessary at ROB, and participant has other adequate medical care in the community.

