## **7 STATISTICAL CONSIDERATIONS**

The study is designed to determine, in a preliminary fashion, whether the quality of high dose rate brachytherapy implants performed in the radiation oncology branch reaches an acceptable level. The quality will be examined separately in four body sites. Specifically, we will stratify by gynecologic (endometrial and cervical), pulmonary, breast, and prostate cancer. In each strata, we will examine the quality of high dose rate brachytherapy with a two-stage optimal design (21). An implant will be considered acceptable if 90% of the GTV receives 90% of the dose prescribed and 80% of the CTV receives 85% of the prescribed dose. An implant will be unacceptable if the above dose limitations are not met.

The two-stage design is based on the following assumptions: (i) the procedure will be considered of poor overall quality (unacceptable) if less than 65% of participants have acceptable implants based on the above criteria ( $P_0=0.65$ ), (ii) the procedure will be considered of good quality (acceptable) if over 90% of participants have acceptable implants based on the above criteria ( $P_1=0.90$ ), (iii) within each stratum, the probability of concluding that an unacceptable procedure is acceptable is less than 4 % ( $\alpha=0.04$ ), and (iv) within each stratum, the probability of concluding that an acceptable procedure is unacceptable is less than 10% ( $\beta=0.10$ ). Based on these operating characteristics, the following two-stage design is optimal. Separately for each of the four strata, the first stage will accrue 9 participants. If 7 or more of the 9 implants have an acceptable implant, then the study will accrue an additional 19 participants. In any stratum, accrual will stop in the first stage if 6 or fewer of 9 participants have an acceptable implant. Assuming that we accrue to the second stage, high dose brachytherapy for a particular tumor type (stratum) will be considered to be acceptably preformed at the clinical center if 23 or more of 28 participants have an acceptable implant.

The error rates stated above are for each of the four strata separately. We note that, with this design, there is less than an 12% chance that one or more strata will falsely conclude that the procedure is acceptable if the procedure is unacceptable in all 4 strata ( $P_0=0.65$ ).

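### Four reasons for stopping treatment also end study follow-up, so the 12-month local control and late toxicity rates may be biased, plausibly towards favourable results

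*Combined protocol and SAP*

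**What the plan says.** Section 3.8 names two statuses, removal from protocol therapy (3.8.1) and off study (3.8.2). Apart from a safety visit at about 30 days, 3.8.1 contains one item: "Protocol therapy is complete when the participant has completed the brachytherapy component of treatment".

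The events that would interrupt or end treatment are all listed under 3.8.2:

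- 3.8.2.2: "Any participant who develops a grade 4 toxicity considered primarily due to the study treatment". The toxicity is then followed for duration and resolution. No time window is given.
- 3.8.2.3, on progression during the active course: the person concerned "will be removed from the study if it is deemed by the PI that additional therapy would not be in the best interest".
- 3.8.2.4: "The development of a concurrent serious medical condition that might preclude or contraindicate the further administration of radiation therapy".
- 3.8.2.5: "The participant is unable to complete the radiation treatment process for any reason", in the same bullet as non-compliance. This section also lists completion of HDR with 12 months of follow-up, and an exit when follow-up at the branch is no longer needed and community care is adequate.

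Section 3.4.2 schedules visits at 1 and 3 months and then every 3 months to 12 months, for participants who have completed protocol therapy. Local control and late toxicity are a secondary objective (1.1.2). Section 7 says that their rates will be tabulated by stratum and overall. It gives no denominator, no censoring rule and no handling of early exits.

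**The concern.** The plan has no status for a participant who has stopped therapy but is still being followed. Someone who meets one of the four criteria leaves the study, and the scheduled assessments of local control and late effects stop. Section 3.4.2 does not clearly cover them either, because its visits follow completion of therapy and 3.8.1 defines completion as finishing brachytherapy. The grade 4 criterion can also apply during follow-up, when no protocol therapy remains to be stopped.

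Toxicity, progression and a shortened course are all plausibly related to later local failure or further late toxicity. If those who leave do worse than those who stay, a rate computed from observed follow-up is too favourable. Scheduled assessments that were never made cannot be restored at analysis. A secondary objective of the study is at stake; no decision rule depends on it.

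**Working it through.** **The plan's own figures.** Section 7 gives no expected rate for local control or late toxicity and no off-study rate, so there is nothing to reproduce on this point. Its figures concern the implant endpoint: poor quality "if less than 65% of participants have acceptable implants based on the above criteria" and good quality "if over 90% of participants have acceptable implants based on the above criteria", with 7 or more of 9 needed to continue and 23 or more of 28 to conclude acceptable. The probability of that conclusion is

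P(accept | p) = Σ over x = 7 to 9 of Bin(x; 9, p) × P[Bin(19, p) ≥ 23 − x].

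This gives 0.0340 at p = 0.65 and 0.9103 at p = 0.90, within the stated limits of 4% and 90% power (100% − 10%). The endpoint is read from the dosimetry of the implant, so losing 12-month follow-up barely touches it. One gap remains: the plan does not say how to handle a participant removed before the implant is evaluated.

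**What is still captured after exit, and what is not.**

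| Item | Captured? | Where |
|---|---|---|
| The triggering grade 4 event | Yes, followed | 3.8.2.2 |
| Local progression already seen on imaging | Yes, counts as local progression | 5.2.1 |
| Serious, related events beyond 30 days | Yes, no off-study exception stated | 5.1 |
| Later local control at scheduled visits | No | 3.4.2, 3.8.2 |
| Scheduled scoring of other late effects | No | 3.4.2, 3.8.2 |

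**Bounds when the outcome after exit is unknown.** Let N be treated, k removed with unknown outcome, and x controlled among the N − k retained. The observed rate is x/(N − k); the rate among all treated lies between x/N and (x + k)/N. The values of k and x are assumptions, with control near 90% in those retained.

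- One stratum, N = 28, k = 3, x = 22: observed 22/25 = 88.0%; bounds 22/28 = 78.6% and 25/28 = 89.3%. The observed rate could be too high by 9.4 points or too low by 1.3.
- All strata, N = 112, k = 11, x = 91: observed 91/101 = 90.1%; bounds 91/112 = 81.3% and 102/112 = 91.1%.

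If one of the 3 removed had documented local progression before exit and it is counted, the upper bound for the stratum falls to (22 + 2)/28 = 85.7%.

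**Bias under an assumed difference.** With retained rate r and removed rate q, the retained-only rate minus the all-treated rate is (k/N)(r − q). Take r = 90% and q from 50% down to 0%:

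| N | k | Bias, percentage points |
|---|---|---|
| 28 | 1 | 1.4 to 3.2 |
| 28 | 3 | 4.3 to 9.6 |
| 28 | 6 | 8.6 to 19.3 |
| 112 | 6 | 2.1 to 4.8 |
| 112 | 11 | 3.9 to 8.8 |
| 112 | 22 | 7.9 to 17.7 |

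If q = r the bias is zero, and if q > r it reverses.

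**Late toxicity.** Suppose 2 grade 3 cases and 1 grade 4 case among 28. Grade 3 or higher is 3/28 = 10.7%. Dropping the grade 4 participant from numerator and denominator gives 2/27 = 7.4%. That fall does not occur if the triggering event is counted, as 3.8.2.2 allows.

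**The case against.** A reader might infer that any progression takes a participant off study. The text does not say so. Section 3.8.2.3 applies only during active treatment and only on the PI's judgement, so progression found at the 3- to 12-month visits is not a trigger. Several courses in Appendix A are short, such as 5 days for primary breast treatment, which leaves little time for this criterion to operate. Concurrent illness and inability to complete are worded around giving radiation, so they too act mainly during treatment.

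A reader might also infer that the reported rates will come from a favourable subset. Section 7 leaves the denominator undefined; it does not restrict it to completers or exclude those off study. Nor is the direction certain: the community-care exit could remove participants who are doing well, and concurrent illness is not shown to predict local failure.

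Finally, the trigger is often an outcome in its own right and can be counted, and 5.1 continues some safety recording. An illustration that gave leavers no recorded failures would therefore overstate the loss.

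All of this stands and limits the point. It does not restore the scheduled local control and late-effect assessments after exit, and the grade 4 criterion has no time limit.

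**Conclusion.** The point holds in a limited form. As written, Section 3.8.2 ends scheduled 12-month assessment for reasons that may be related to outcome, and Section 7 does not say how such participants enter the tabulation. The local control and late toxicity rates may be biased, plausibly towards favourable results.

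The size cannot be stated, because the documents give neither a removal rate nor outcomes after removal. The figures above show scale only and rest on assumed numbers of removals and assumed control rates. The effect is confined to descriptive secondary results. It should be corrected, but it does not threaten the primary conclusion on implant quality.

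**What to change.** 1. Move 3.8.2.2, 3.8.2.3, 3.8.2.4 and the inability-to-complete item of 3.8.2.5 (splitting that bullet) to 3.8.1 as reasons to end protocol therapy. This changes follow-up status only; when therapy ends stays as it is.
2. Keep these participants on study for the Section 3.4.2 visits to 12 months where consent allows, and reword 3.4.2 so that it covers participants who stop early.
3. Leave the other off-study criteria in place: administrative reasons, including loss of capacity to consent and PI best interest; the community-care exit; and death. Narrowing off study to a short list would remove some of these, including a participant protection, without discussion.
4. In Section 7, state that local control and late toxicity are tabulated over all treated participants, that events before exit are counted, and that early exits are reported by number and reason.

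The cost is amendment wording and a few additional visits of a type already scheduled.

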### 3.8.2.3 Tumor Progression

Any participant with clinical or radiographic evidence of progressive disease during the active course of treatment will be removed from the study if it is deemed by the PI that additional therapy would not be in the best interest of the participant.

### 3.8.2.4 Concurrent Illness

The development of a concurrent serious medical condition that might preclude or contraindicate the further administration of radiation therapy.

### 3.8.2.5 Completion

- The completion of HDR and 12 months follow up
- The participant is unable to complete the radiation treatment process for any reason or is non-compliant with the treatment &/ or follow- up requirements
- Follow-up is no longer deemed necessary at ROB, and participant has other adequate medical care in the community.

### 3.8.2.6 Death

## 4 CONCOMITANT MEDICATIONS/MEASURES

### 4.1 SUPPORTIVE CARE

Most participants are expected to receive their standard supportive care by their referring oncologists. Occasionally, however, participants may not have timely or appropriate access to supportive care at home, and in these rare cases, supportive care will be provided at the NIH Clinical Center. Examples of such care include, but are not limited to, the management of acute radiation effects/complications, steroid medication, conscious sedation, analgesics, anti-emetics, and intravenous hydration.

### 4.2 CONCURRENT THERAPIES

No investigational drugs or therapies will be administered by NCI ROB personnel in this protocol. However, the participant may be receiving other appropriate cancer therapy based on standard practice. This will be coordinated by the referring oncologist.

## 5 DATA COLLECTION AND EVALUATION

### 5.1 DATA COLLECTION

The PI will be responsible for overseeing entry of data into an in-house password protected electronic system (C3D) and ensuring data accuracy, consistency and timeliness. The principal investigator, associate investigators/research nurses and/or a contracted data manager will assist with the data management efforts. All data obtained during the conduct of the protocol will be kept in secure network drives or in approved alternative sites that comply with NIH security standards. Primary and final analyzed data will have identifiers so that research data can be attributed to an individual human subject participant.

- Clinical data and acquired images will be recorded in a NCI CCR database (C3D).
- Clinical data collection will include: demographic information, pathologic diagnosis, clinical stage, history including prior and concurrent therapies, location and measurement of lesions, CT reports, lab reports, vital signs, dose of radiation delivered, and toxicity assessment.
- The results of any procedures and/or tests will be included in the participants' hospital chart and/or research records as appropriate. Data from these records may be used in research and scientific publications.
- Data collected may be used anonymously, for publications not originally specified, concerning the disease processes and long term effects of treatment. The data may also be used as the basis for new protocols.

All AEs, including clinically significant abnormal findings on laboratory evaluations, regardless of severity, will be followed until return to baseline or stabilization. Document AEs from the first study intervention through 30 days after the intervention was last administered. Beyond the 30 days after the last intervention, only adverse events which are serious and related to the study intervention need to be recorded.

An abnormal laboratory value will be considered an AE if the laboratory abnormality is characterized by any of the following:

- Results in discontinuation from the study
- Is associated with clinical signs or symptoms
- Requires treatment or any other therapeutic intervention
- Is associated with death or another serious adverse event, including hospitalization.
- Is judged by the Investigator to be of significant clinical impact
- If any abnormal laboratory result is considered clinically significant, the investigator will provide details about the action taken with respect to the participant's outcome.

**End of study procedures:** Data will be stored according to HHS, FDA regulations and NIH Intramural Records Retention Schedule regulations as applicable.

**Loss or destruction of data:** Should we become aware that a major breach in our plan to protect subject confidentiality and trial data has occurred, this will be reported expeditiously per requirements in section **6.2.1**.

## 5.2 RESPONSE CRITERIA

Tumor Response for Solid Tumors: In diseases where targets can be imaged, response will be measured using the RECIST criteria only for local sites as this is not a trial of a systemic therapy. Response will be scored for each target lesion. Every effort should be made to objectively record changes in the participant's disease process after the HDR procedure. Measurable criteria should always take precedence over subjective criteria.

### 5.2.1 Evaluation of target lesions

In diseases where targets can be imaged, the target lesion is defined as the sites which are targeted with HDR as part of this protocol. The response will be measured with margins defined

as the longest diameter measurement on the appropriately specified radiographic imaging. The imaging modality will be that which provided the maximal measurement pretreatment. This imaging modality will be used at each follow-up to determine local control. If there is evidence of clinical progression, the imaging study will be repeated to assess for progression.

- Complete Response (CR): Complete disappearance of the target lesion.
- Partial Response (PR): at least a 30% decrease in the sum of the longest diameter (LD) of the target lesion taking into account the baseline sum LD
- Stable/No Response: Does not qualify for CR, PR, or progression.
- Progression: Interval increase in the maximal dimension of the target lesion.
- Local Control: will be defined as CR, PR, or stable disease of the treated site (s). Local progression on any imaging modality (bone scan, MRI, CT, or PET) obtained during the normal course of therapy and follow-up will be considered locally progressive disease.

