#### **3.4.2 Post-Active Treatment Phase**

- Following completion of protocol therapy, participants will be seen in follow-up. Follow-up evaluations should occur at NIH at one month after the completion of radiation therapy, at three months after completion of radiation therapy, followed by every 3 month intervals up to 12 months
- Follow- up evaluations will include:
  - Clinical Evaluation- complete interval history and directed physical examination, notation of any ongoing or recently delivered systemic therapy
  - Any medical procedures/tests will be based on the participant's diagnosis, treatment, and supporting clinical information.
  - Assessment of acute and long-term effects of radiation therapy using the RTOG and CTC 4.0
  - In diseases where targets can be imaged, CT, MRI, or other appropriate imaging of the tumor site(s). In general, CT will be the preferred imaging modality unless the lesion is not visible on this modality. PSA will be adequate for follow up in prostate participants unless otherwise indicated.
  - Scoring of local control at each treated site will be based on RECIST criteria (limited to local disease status). Each site will be scored separately.

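### Section 5.2.1 lets only imaging register a local failure, so a treated-site recurrence proven by pathology or seen directly, without progression on any imaging, is tabulated as local control

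*Combined protocol and SAP*

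**What the plan says.** Section 5.2.1 applies to diseases whose targets can be imaged. Response is measured "as the longest diameter measurement on the appropriately specified radiographic imaging", using the modality that gave the largest pretreatment measurement. Of that modality the section says: "This imaging modality will be used at each follow-up to determine local control".

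The failure category is "Progression: Interval increase in the maximal dimension of the target lesion". No minimum size of increase is given. The section adds one further route to failure: local progression on a bone scan, MRI, CT or PET scan obtained in ordinary care. Clinical evidence is handled in one sentence: "If there is evidence of clinical progression, the imaging study will be repeated to assess for progression".

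The residual category is "Stable/No Response: Does not qualify for CR, PR, or progression". Local control is then the union of complete response, partial response and stable disease.

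Two other places bear on scoring. Section 5.2 says: "Measurable criteria should always take precedence over subjective criteria". Section 3.4.2 scores local control at each treated site by RECIST, restricted to local disease. It also lists, for every follow-up visit, "Clinical Evaluation- complete interval history and directed physical examination".

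Local control is a secondary objective (section 1.1.2). Section 7 tabulates it by stratum and over all four strata combined.

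**The concern.** Several eligible sites can be inspected or biopsied directly: the vaginal cuff, the intact cervix, the inoperable uterus and the endobronchial airway. At these sites a recurrence may be established by biopsy, or seen at endoscopy or speculum examination, while the scan shows no change. The categories in section 5.2.1 give such an event no way to become a failure. The protocol will often hold the evidence, since the visit includes an examination and section 5.1 puts procedure and test results in the hospital chart or research records. The endpoint rule does not use it.

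What is at stake is the meaning of the local control rate, the main disease outcome that the study will report. A rate that can include biopsy-proven local recurrences as controlled is not what a reader would take the term to mean. The alternative is that scorers depart from the written rule case by case.

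**Working it through.** The plan states no expected local control rate and no precision target for it, so there is no figure to reproduce. The check has three steps.

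**Step 1. Follow one case through the rules.** Take a participant with a measured baseline lesion and a biopsy-proven recurrence at the treated site during follow-up.

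| Rule | Result for this case |
|---|---|
| Clinical progression (5.2.1) | Scan is repeated; no event recorded |
| Increase in maximal dimension (5.2.1) | Not met if the repeat scan shows no increase |
| Local progression on bone scan, MRI, CT or PET (5.2.1) | Not met if no such scan shows it |
| Complete response, partial response or stable (5.2.1) | One of these applies by default |
| Local control (5.2.1) | Yes |

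The same holds if the lesion had disappeared on imaging and the recurrence is found only on the mucosa: the imaging category stays complete response. Nothing in sections 3.4.2, 5.2 or 7 reverses the result. The exact condition is no progression on any imaging. It is not merely no measured growth, because bone scan or PET progression counts without a stated size criterion.

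**Step 2. Size per case.** The denominators are the section 7 maxima: 28 per stratum and 112 overall. Assume one scored site per participant. Reclassifying k participants from control to failure lowers the rate by 100 × k / n points. The documents give no value for k, so 1 to 3 is an assumption.

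| k | n = 28 | n = 112 |
|---|---|---|
| 1 | 100 × 1/28 = 3.6 | 100 × 1/112 = 0.9 |
| 2 | 100 × 2/28 = 7.1 | 100 × 2/112 = 1.8 |
| 3 | 100 × 3/28 = 10.7 | 100 × 3/112 = 2.7 |

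In a stratum that stops after its first stage of 9, one case is 100 × 1/9 = 11.1 points.

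As an illustration, suppose all 28 would otherwise be scored as controlled. With exact 95% intervals the rate is then:
- k = 0: 28/28 = 100% (87.7 to 100)
- k = 1: 27/28 = 96.4% (81.7 to 99.9)
- k = 2: 26/28 = 92.9% (76.5 to 99.1)
- k = 3: 25/28 = 89.3% (71.8 to 97.7)

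The shift from one case is small against the width of these intervals.

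**Step 3. Net direction.** Let A be the recurrences scored as controlled by this gap. Let B be the participants scored as failures because of a size increase that is not regrowth, such as measurement variation. Then reported rate − true rate = (A − B)/n. Section 5.2.1 sets no minimum increase, so B need not be zero. The documents give neither A nor B, so the sign is undetermined.

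**The case against.** The strongest defence is that imaging-based scoring is a deliberate choice of objectivity. The study has a single arm and the treating branch scores its own results, so keeping judgement out of the endpoint has value. The net is also wide: any increase in size counts, progression on any of several modalities counts, and clinical progression prompts another scan. To be missed, a recurrence must escape all of these. This stands as a reason to expect few cases. It does not justify scoring a pathology-proven recurrence as controlled, and pathology is not plainly subjective evidence under section 5.2.

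It is also fair that the documents nowhere say in words that a proven recurrence is local control. The result follows from the residual stable category and from scoring that turns on imaging. Section 5.2 sets an order of precedence; it does not exclude other evidence.

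The denominator of 28 is a ceiling. The gynecologic stratum admits post-operative participants who may have no measurable lesion. With fewer scored participants, each case weighs more than 3.6 points.

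Three stronger readings are tempting, and the documents do not support them:

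- **A contradiction with section 3.8.2.3.** That section removes "Any participant with clinical or radiographic evidence of progressive disease during the active course of treatment", so a reader might infer that the same person can be removed for progression yet counted as controlled, in conflict with the plan. But the rule covers only active treatment, depends on the investigator's judgement about further therapy, is not limited to the treated site and does not feed the endpoint. Removal for progression elsewhere with the treated site controlled is coherent.
- **A rate biased upward overall.** Step 3 shows that the sign cannot be determined.
- **Strata that cannot be compared.** The plan compares no strata; it only tabulates them.

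**Conclusion.** The point holds in a limited form. For imaged targets, the written rules tabulate a treated-site recurrence as local control when it is proven by pathology, or directly visualised, and no imaging shows progression. Each case adds 3.6 points in a full stratum of 28 and 0.9 points in 112, assuming maximum accrual and one scored site per participant. The number of cases is not given, and the net bias of the rate is unknown.

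This concerns a descriptive secondary endpoint. The implant-quality decision, the two-stage design and the sample size do not depend on it. The change is still worth making, because a proven local recurrence reported as local control is a wrong classification and the correction is cheap.

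**What to change.** In section 5.2.1, define local progression as either of the following:

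1. Imaging progression of the treated site, as now.
2. Recurrence at the treated site confirmed by pathology, or directly visualised tumor recorded as local progression, found in care the participant receives anyway.

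Date the event at the first such evidence. Do not count clinical suspicion that has no such confirmation. Report the number of failures by route, so that the imaging-only rate stays visible. Align the RECIST scoring sentence in section 3.4.2 and the precedence sentence in section 5.2, so that neither can be read as overriding the second route.

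The pathology part is the firm core. Direct visualisation without biopsy involves more judgement, and reporting by route lets readers set it aside. Endoscopy is not a scheduled follow-up procedure, so detection by this route will vary with ordinary care.

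The cost is a short edit in three places. No procedure is added and treatment does not change. The downside is slightly more judgement in scoring and possibly a lower reported rate.
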